8.5 Safety Analysis

The safety population will include all subjects in the Intent to Treat Population treated with the Interscope EndoRotor® device. Only monitored data, including safety data confirmed by review of source documents, will be entered into the database for statistical analysis. All serious adverse events will be adjudicated by an Independent Physician Adjudicator serving as the Data Monitoring Committee for safety. Reports of SAE adjudication will be included in the final analysis and clinical report.

8.6 Secondary Endpoint Analysis

The secondary endpoints will be characterized using descriptive statistics.

8.7 Site Poolability

Due to the small number of subjects anticipated to be enrolled at each site, which would result in underpowered testing of site differences, poolability over site will not be tested. Data will be pooled over sites for analysis.

8.8 Sample Size

With a sample size of 60 and a success rate of 0.85, we can expect the 95% exact confidence interval to be between 0.782 and 0.967. Our goal is to achieve a confidence interval half width of our point estimate that is not greater than 0.10. The proposed sample size of 60 will provide a

confidence interval half width 0.0972, and so will meet the targeted precision for our point estimate. Further, because this study is a post-market, confirmatory, observational study, the sample size identified is consistent with post-market studies of similar devices.

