8.4 Primary Endpoint Analysis

The primary analysis will be completed on the Per Protocol population and will consist of all evaluable subjects enrolled in the study who have documented recurrent flat or sessile colorectal lesions up to 6 cm in diameter and/or length and are treated with the Interscope device without adjunctive modality. The analysis will be conducted on the percent of lesions with persistent disease. The primary endpoint is:

Technical Success, defined as the ability of the EndoRotor device to resect recurrent flat or sessile colorectal lesions without concomitant use of other resection modalities for mucosectomy and no definitely and probably device-related serious adverse events (SAEs) throughout the 90-day follow-up period.

This analysis population will be used to describe the primary effectiveness and the secondary endpoints. A confidence interval for the successful removal of all lesions will be calculated by Clopper-Pearson exact methods⁶ if all subjects are treated for one lesion. In the event that one or more subjects are treated for multiple lesions, then a generalized estimating equation with a logistic link function will be used to estimate the 95% confidence interval of the success rate.

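### The expected confidence interval in section 8.8 (0.782 to 0.967) does not follow from its stated inputs; 60 subjects and a rate of 0.85 give 0.734 to 0.929

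*Combined protocol and SAP*

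**What the plan says.** Section 8.8 (Sample Size) justifies the sample size by precision. Its inputs are given in one phrase: "With a sample size of 60 and a success rate of 0.85". From these it states that "we can expect the 95% exact confidence interval to be between 0.782 and 0.967". It then sets the target, "Our goal is to achieve a confidence interval half width of our point estimate that is not greater than 0.10", and reports that 60 subjects give a "confidence interval half width 0.0972", which it judges sufficient.

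Section 8.4 (Primary Endpoint Analysis) names the exact method: "A confidence interval for the successful removal of all lesions will be calculated by Clopper-Pearson exact". This applies when every subject is treated for one lesion. If any subject has more than one, the interval comes from a generalized estimating equation (GEE) instead.

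Section 8.0 describes the analysis as mainly descriptive. Section 8 sets no hypothesis test and no performance goal.

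**The concern.** The printed limits look wrong before any software is used. They lie 0.85 − 0.782 = 0.068 below the assumed rate and 0.967 − 0.85 = 0.117 above it. An exact binomial interval for a rate above one half has its longer arm on the lower side, so the asymmetry runs the wrong way. Half the distance between the limits is also not the half-width reported in the same paragraph.

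What is at stake is the precision that the plan promises. In a single-arm study with no performance goal, the lower limit tells a reader how poor a true success rate would still be compatible with the result. The printed figure makes that limit more favourable than the design can deliver at the assumed rate. If the trial observes 51 of 60, the reported interval will visibly fail to match the plan.

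**Working it through.** **Inputs**

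- n = 60 and success rate 0.85 (section 8.8). 0.85 × 60 = 51 exactly, so x = 51 and rounding plays no part.
- 95% confidence, exact (section 8.8). Two limits are given, so it is two-sided with 0.025 in each tail.
- Exact method: Clopper-Pearson (section 8.4).
- Target half-width at most 0.10; stated half-width 0.0972 (section 8.8).

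**Formula**

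- Lower limit = 0.025 quantile of Beta(x, n − x + 1) = Beta(51, 10)
- Upper limit = 0.975 quantile of Beta(x + 1, n − x) = Beta(52, 9)

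**Step 1. Try to reproduce the plan's interval.** The result is 0.7343 to 0.9290, not 0.782 to 0.967.

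| | Plan | Recomputed, 51/60 | Difference |
|---|---|---|---|
| Lower limit | 0.782 | 0.7343 | 0.0477 |
| Upper limit | 0.967 | 0.9290 | 0.0380 |
| Half-width from the limits | (0.967 − 0.782)/2 = 0.0925 | 0.0974 | −0.0049 |
| Half-width as stated | 0.0972 | 0.0974 | −0.0002 |

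The stated half-width fits the stated inputs; the stated limits fit neither the inputs nor the half-width.

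**Step 2. Try another method on the same inputs (51/60).** None gives the printed pair:

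| Method | Limits |
|---|---|
| Wald | 0.760 to 0.940 |
| Wald, continuity-corrected | 0.751 to 0.949 |
| Wilson | 0.739 to 0.919 |
| Agresti-Coull | 0.737 to 0.921 |
| Jeffreys | 0.744 to 0.923 |
| Inverted exact binomial test | 0.735 to 0.922 |
| Clopper-Pearson, 90% | 0.753 to 0.919 |
| Clopper-Pearson, 80% | 0.774 to 0.907 |

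**Step 3. Read the statement as an expectation.** Averaging the Clopper-Pearson limits over Binomial(60, 0.85) gives 0.7356 to 0.9275, half-width 0.0960. This does not explain the printed pair either.

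**Step 4. Try another success count out of 60.** No count from 0 to 60 gives both limits. The nearest are 53/60 (0.7743 to 0.9518) and 54/60 (0.7949 to 0.9624).

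**Step 5. Try other sample sizes.** Over all counts for n = 20 to 149, one Clopper-Pearson interval equals the printed limits to three decimals: 45/50, rate 0.90, with 0.7819 to 0.9667 and half-width 0.0924. The next nearest, 46/51, gives 0.7859 to 0.9674. The printed pair is therefore a valid exact interval for other inputs, which makes garbled digits an unlikely explanation. That it was carried over from a calculation with n = 50 and rate 0.90 is an inference; the documents do not say so.

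**Step 6. Check the target.** Half of the total width at 51/60 is 0.0974, below 0.10. The two arms are 0.85 − 0.7343 = 0.1157 below and 0.9290 − 0.85 = 0.0790 above.

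**The case against.** The best case for leaving this alone is that nothing depends on the limits. The criterion that sets the sample size is the half-width, and 0.0972 is correct to within 0.0002. Section 8.8 also appeals to the size of post-market studies of similar devices. There is no hypothesis, performance goal or interim look for the lower limit to affect, and the final report will compute its own interval from the data. All of this stands. It limits the consequence, but it does not make the printed limits right.

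Three further points deserve an answer.

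- **The exact interval is asymmetric.** Its lower arm, 0.1157, exceeds 0.10, so the target is met only if half-width means half of the total width. That is the natural reading and the one that fits the plan's 0.0972, but the condition should be recognised.
- **Clopper-Pearson applies only when each subject has one lesion.** With multiple lesions section 8.4 moves to GEE, and the corrected limits are then a planning approximation. This does not rescue the printed pair, because section 8.8 itself calls its interval exact.
- **The 45/50 match raises the question of which inputs were intended.** The stated half-width supports 60 and 0.85, so the correction is very probably right, but the sponsor should confirm it.

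**Conclusion.** The concern holds. For 60 subjects and a rate of 0.85, the exact 95% interval is 0.734 to 0.929. The printed limits overstate the lower end by 4.8 percentage points and the upper end by 3.8, and they contradict the half-width given beside them. No alternative method, count out of 60 or reading as an expected interval that was tried reproduces them.

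The error is confined to the precision that the plan states. The sample size of 60 and the planned analysis are unchanged, and the 0.10 target is still met. This rests on three assumptions: 60 subjects are analysed, each contributes one lesion, and half-width means half of the total width. The point should be fixed because it is a plain error in the sample-size justification and it errs in the favourable direction, but it does not undermine the design.

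**What to change.** In section 8.8, replace the limits 0.782 and 0.967 with 0.734 and 0.929. Change the half-width from 0.0972 to 0.0974 so that it matches the new limits; that second change is cosmetic. Before editing, the sponsor should confirm that 60 and 0.85 are the intended planning values, since the printed limits are those of 45/50. A short note that half-width means half of the total interval width would remove the ambiguity from the asymmetry.

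The cost is one corrected sentence. No subjects are added and no analysis changes. The stated limits become less favourable.

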8.9 Handling of Missing Data

Missing data for the primary effectiveness endpoint will be dropped from the analysis of that endpoint. Safety endpoints, as is standard, will not be imputed.

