4.0 STUDY ENDPOINTS AND SUBJECT POPULATION

4.1 Primary Endpoints

Primary Effectiveness Endpoint (Performance):

Technical Success, defined as the ability of the EndoRotor device to resect recurrent flat or sessile colorectal lesions without concomitant use of other resection modalities for mucosectomy and no definitely or probably device-related serious adverse events (SAEs) throughout the 90-day follow-up period.

Primary Safety Endpoint:

Assessment of Serious Adverse Events (incidence, relationship to device and severity) at index procedure and at 90 days, post-procedure.

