5.3 Subject Enrollment and Withdrawal

All subjects requiring interventional colonoscopy for colon polyps are potential study candidates and will be screened for eligibility. Every effort will be made to ensure eligibility of the participants prior to study procedure. Actual enrollment in the study occurs at the time of informed consent.

Subjects who do not meet all inclusion / exclusion criteria (e.g., including inability to reach the target area or colon anatomy not conducive to tissue resection) will be considered a screen failure and will not be followed in the study (no data will be collected on these subjects). Subjects in whom the Interscope EndoRotor® is inserted into the colon and resection is attempted, but the procedure is aborted without resection of tissue, will be followed through discharge for safety. At discharge, the subject will be assessed for safety only and the subject will be allowed to exit the study.

Subjects may withdraw at any time from the clinical study without jeopardy or prejudice. If a subject prematurely terminates from the study, the reason for study termination will be recorded and the results will be tabulated by number and percent for each category. If termination is the result of an adverse event or death, an Adverse Event Form will also be completed. Subjects who withdraw consent after treatment will have their data evaluated until the time of their withdrawal

The Investigator should follow all unresolved serious adverse events until the events are resolved, the subject is lost to follow-up, the subject has withdrawn consent, or the adverse event is otherwise explained.

All reasonable efforts will be made to obtain complete data for all subjects; however, missing medical observations will occur due to loss to follow-up, withdrawal, or non-adherence with required assessments. If a subject cannot be located, they will be considered lost to follow-up. If they are contacted but refuse to return for visits or they actively request to withdraw from the study, they will be considered withdrawals. Data collected up to the time of lost to follow-up, and withdrawal of consent will be maintained in the study database and used for analysis purposes, as appropriate. These subjects will not be replaced.

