5.4 Anticipated Total Enrollment

It is anticipated that sixty (60) evaluable patients will be enrolled. Loss to follow-up is anticipated to be no more than 10%.

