5.7 Index Procedure

All patients will receive the EndoRotor® treatment following the technique described by Interscope's Instructions for Use.

The mucosal resections are performed during standard flexible colonoscopy procedures. All medications given, pre- and post-procedure precautions and follow-up assessments are part of routine standard of care. This protocol concerns itself with the actual removal of the mucosal lesion once the abnormal area is identified using the colonoscope.

- Patients will be prepped in the usual manner for lower GI endoscopy prior to their interventional visit.
- The procedures will be performed with either Propofol sedation or under general anesthesia.
- When a mucosal lesion is found, the EndoRotor® system will be prepared by attaching the EndoRotor® catheter, foot pedal and the calibrated suction to the Control Unit, ensuring there is a filter in the collection unit (specimen trap), and then priming the catheter with 0.9% normal saline.
- Lesions will be injected using saline solution with dye such as Indigo carmine or Methylene Blue. Indelible ink (such as SPOT) will be injected into the region of the resection to identify the site after resection.
- The EndoRotor® catheter will be inserted through the working channel of the endoscope until it is in proper cutting position with the cutting surface oriented towards the mucosal lesion and the catheter no more than 3cm out of the scope. The physician will turn the motor on by depressing the blue pedal and engage cutting by holding the orange pedal for as long as he/she wishes to cut tissue.
- Cutting should be performed while moving the EndoRotor® catheter. The endoscopist will take care to not keep the suction activated when he/she is not intending to cut mucosa and when stopped for more than 1 second while apposed to tissue to not risk creating a perforation.
- Various techniques can be used to remove the lesion. Recurrent, flat or sessile lesions will be attempted to be removed entirely with the EndoRotor® with no other treatment modalities. The physician will utilize the recommended technique appropriate to the lesion until there is no longer visible evidence of mucosal lesion. The intent of the protocol is to complete lesion resection using the EndoRotor as the only treatment modality. However, should it prove not feasible to complete the resection with the EndoRotor, the investigator may convert to the use of an alternative resection modality.

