8.2 Analysis Populations

Two analysis populations are defined for this protocol, Intent to Treat and Per Protocol.

Intent to Treat Population: All subjects in whom the EndoRotor was used for any resection of a lesion. This includes those subjects that were either treated with the EndoRotor alone or with another adjunctive modality.

Per Protocol (PP): Subset of the Intent to Treat population including those subjects who had complete lesion resection with the EndoRotor alone without any adjunctive modality resection, did not have inclusion/exclusion protocol deviations and completed the 90 day follow up visit. The effectiveness analyses will be conducted on the per protocol population.

Safety Population: Defined as all subjects who were treated with the device.

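### The Per Protocol definition, with a missing-data rule silent on observed failures, removes known failures from the primary technical-success analysis

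*Combined protocol and SAP*

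**What the plan says.** All references are to the combined protocol and SAP.

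- **Endpoint (4.1).** Technical Success is resection of the recurrent lesion "without concomitant use of other resection modalities for mucosectomy and no definitely or probably device-related serious adverse events (SAEs) throughout the 90-day follow-up period".
- **Primary population (8.4).** "The primary analysis will be completed on the Per Protocol population".
- **Per Protocol definition (8.2).** Subjects must have had "complete lesion resection with the EndoRotor alone without any adjunctive modality resection", and they must be subjects who "did not have inclusion/exclusion protocol deviations and completed the 90 day follow up visit".
- **Conversion (5.7).** If the resection cannot be finished with the device, "the investigator may convert to the use of an alternative resection modality".
- **Aborted cases (5.3).** These are subjects in whom resection was attempted but no tissue was removed. "At discharge, the subject will be assessed for safety only and the subject will be allowed to exit the study". The Intent to Treat set in 8.2 requires that the device was used for some resection, so these subjects are outside it.
- **Missing data (8.9).** "Missing data for the primary effectiveness endpoint will be dropped from the analysis of that endpoint". Missing is not defined, and no sensitivity analysis is planned.
- **Data before loss or withdrawal (5.3).** They are kept and used as appropriate, with no further rule.
- **Expected loss (5.4).** "Loss to follow-up is anticipated to be no more than 10" per cent.

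**The concern.** The endpoint is a composite in which one observed failure component decides the outcome. The 90-day visit is needed to confirm a success; it cannot reverse a failure. A primary population that requires both EndoRotor-only complete resection and the visit is therefore selected partly on the outcome that it is meant to estimate.

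Three groups of known failures are affected: converted subjects, subjects with a definitely or probably device-related SAE who do not complete the visit, and aborted resections. Inside the Per Protocol set, the only failure that can still be counted is such an SAE in a subject who returns at 90 days. The modality component of the endpoint is met by construction.

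At stake are the headline effectiveness percentage and its confidence interval, which would describe selected subjects rather than the performance of the device when its use is attempted.

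**Working it through.** **Inputs.** N = 60 and success rate 0.85, so 51 successes and 9 failures (8.8). Loss of at most 10%, applied as 6 of 60 (5.4). Clopper-Pearson interval (8.4). Target half-width at most 0.10 (8.8). The split of the 6 between known failures and event-free subjects is not in the documents, so it is varied.

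**The plan's own figure.** Clopper-Pearson for 51/60 gives 0.734 to 0.929, half-width 0.0974. This agrees with the stated half-width of 0.0972 to within 0.0002. The stated interval, 0.782 to 0.967, is not reproduced. That is a separate matter and does not affect what follows.

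**Step 1: subjects without the 90-day visit.** Let k of the 6 be known failures, and assume that the other 6 − k are event-free and truly successes. The observed successes are s = 51 − (6 − k).

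- Dropping all 6: s/54.
- Keeping the known failures: s/(54 + k).

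| k | Drop all 6 | Keep known failures | Difference (points) |
|---|---|---|---|
| 0 | 45/54 = 83.3% | 45/54 = 83.3% | 0 |
| 1 | 46/54 = 85.2% | 46/55 = 83.6% | 1.5 |
| 3 | 48/54 = 88.9% | 48/57 = 84.2% | 4.7 |
| 6 | 51/54 = 94.4% | 51/60 = 85.0% | 9.4 |

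Differences are taken before rounding. At k = 0 the complete-case rate is 83.3% against a true 85.0%, so losing event-free subjects can also lower the estimate.

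**Step 2: conversions, with no missing data.** If m of the 9 failures are conversions, the Per Protocol rule gives 51/(60 − m):

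- m = 3: 51/57 = 89.5%
- m = 6: 51/54 = 94.4%
- m = 9: 51/51 = 100%

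No change to section 8.9 alone would alter these figures.

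**Step 3: bounds for a complete-case result.** Suppose 46 of 54 succeed and 6 outcomes are truly unknown.

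- Complete-case: 46/54 = 85.2% (exact 95% CI 72.9 to 93.4%). The half-width of 0.1025 misses the 0.10 target.
- Missing = failure: 46/60 = 76.7% (64.0 to 86.6%).
- Missing = success: 52/60 = 86.7% (75.4 to 94.1%).

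The fall of 85.2 − 76.7 = 8.5 points is a worst-case bound, not an expected bias.

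**The case against.** **Section 8.9 does not say that known failures are dropped.** A reader might infer that it does. It drops missing outcomes, and under 4.1 a conversion or a qualifying SAE makes the outcome known. Section 5.3 also keeps data collected before loss. This stands: 8.9 is silent, not wrong on its face. But use as appropriate is discretion rather than a rule, and the Per Protocol definition removes these subjects on any reading of 8.9.

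**Technical success is not shown to be biased upward overall.** A reader might infer that too. The direction is certain only for known failures that are removed. Nothing in the documents links loss to failure, and nothing says that converted subjects leave follow-up; they are excluded with or without missing data.

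**The visit may be needed for another outcome.** Section 8.4 also refers to the percentage of lesions with persistent disease, which does need the 90-day endoscopy. That can justify the visit requirement for persistence, but not for a technical-success failure already observed.

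**The SAEs are not hidden.** After a resection, a device-related SAE stays in the safety population, is adjudicated and counts in the primary safety endpoint. This stands: the gap concerns the effectiveness percentage.

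**The analysis is mainly descriptive.** Section 8.0 says so, and no success threshold is set, so no formal conclusion turns on the rate. This lowers the consequence but does not make the percentage a fair estimate.

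**Conclusion.** The concern holds, with sections 8.2 and 8.4 as the operative cause and 8.9 as a missing safeguard. As written, the plan takes known failures out of the primary technical-success analysis, and doing so can only raise the reported rate.

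The size depends on facts the plan does not give. With 51/60 true successes and 6 subjects without the visit, the inflation from dropping known failures runs from 0 to 9.4 points. Three such subjects (4.7 points) would use about half of the 0.10 target half-width. Exclusion of conversions acts separately and could bring the rate to 100% if every failure were a conversion.

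These figures rest on two assumptions: that 10%, a ceiling, is reached, and that it applies to 60 treated subjects. The plan speaks of 60 evaluable subjects. If 60 must remain after loss, 60/0.90 = 66.7, so 67 would be enrolled; the mechanism is the same. The documents do not support 8.5 points as an expected bias.

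**What to change.** Amend 8.2, 8.4 and 8.9 together. Changing 8.9 alone would leave the primary result as it is, because the affected subjects are already outside the Per Protocol set.

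1. Analyse technical success in all subjects in whom EndoRotor resection was attempted, including aborted cases. Count conversion to another resection modality, aborted resection, or a definitely or probably device-related SAE as failure, whether or not the 90-day visit took place. Keep the existing statement in 5.7 that techniques used only for hemostasis are not an alternative modality.
2. Treat as missing only event-free subjects without 90-day data.
3. Report the complete-case rate with missing = failure and missing = success bounds. With k = 3 in the illustration, this would be 48/57 = 84.2%, with bounds 48/60 = 80.0% and 51/60 = 85.0%.
4. Keep the present Per Protocol result as a supportive analysis.

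The cost is SAP wording and a few table rows. Procedure outcome and SAEs are already recorded, so the failure rule needs no new assessment. The reported rate may be lower.
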